1.1 Study Objectives

1.1.1 Objectives

Objective 1: To develop and refine PICT, an intervention to train family caregivers of PWD how to administer an observational pain assessment tool and communicate the results to health care providers.

Objective 2: To evaluate the feasibility and acceptability of the finalized version of PICT among family caregivers of PWD and health care providers

Objective 3: To test the preliminary efficacy of PICT on 1) caregiver ability to identify pain symptoms; and 2) caregiver efficacy in communicating with health care providers

1.1.2 Hypotheses / Research Questions

Hypothesis 1: As this study objective involves intervention development only, no hypotheses are given.

Hypothesis 2a (feasibility): 70% or more of participants will meet the benchmark for feasibility, defined by participant retention and adherence to the intervention.

Hypothesis 2b (acceptability): 70% or more of participants will meet the benchmark for acceptability, defined by participant ratings on questionnaires related to “helpfulness,” “future use,” and “overall comprehension” of the intervention content.

Hypothesis 3: PICT will be more effective than an attention control for improving caregivers’ ability to identify pain in PWD and to initiate pain related-communication with health care providers.

2. Background and Significance

Dementia afflicts more than 5 million older adults (ages 65 and older) in the United States,¹ the majority of whom reside in the community.² Up to 60% of affected individuals suffer from pain,^{3,4} with similar prevalence estimates across dementia subtypes (e.g., Alzheimer’s disease, vascular dementia).⁵ Although best practice guidelines have emphasized the importance of routine pain assessment of older persons with dementia (PWD),⁶ pain remains severely under-detected and undermanaged in this population.^{7,8} Untreated pain has profound effects on individuals’ quality of life,^{9,10} and is associated with numerous adverse outcomes, including physical impairment,¹¹ depression,^{12,13} social isolation,^{14,15} increased health service use,¹⁶ and disruptions to family functioning.^{17,18} One of the greatest barriers to detecting and treating pain in PWD is impaired communication.¹⁹ As dementia progresses, the capacity to communicate effectively about one’s pain diminishes;²⁰ individuals may be unable to understand or verbally articulate their discomfort, and instead express their pain through non-verbal behaviors (e.g., facial expressions, agitation).²¹ In such cases, self-reports of pain are not feasible and behavioral assessment is recommended.^{22,23} Family caregivers (spouses; adult children; other close relatives) are well situated to detect PWD’s pain symptoms and communicate those symptoms to health care providers. Nearly 80% of community-dwelling PWD receive help from a caregiver.^{24,25} These caregivers are in frequent, if not constant, contact with PWD²⁶ and are highly involved in their disease management activities.^{27,28} Unlike health care providers who are likely to see the patient in a single

context (the treatment visit), caregivers have the opportunity to observe the PWD in diverse situations (e.g., at rest, during transfers, after the administration of pain medication), which is necessary not only for identifying the presence of pain, but also for determining under what circumstances it is likely to occur. Caregivers have frequent opportunities to communicate their observations to providers as companions to PWD at their doctor's visits.^{29,30} Indeed, providers commonly turn to family members who are familiar with the patient for help interpreting the patient's pain,³¹⁻³³ but caregivers are sometimes reluctant to bring up pain-related concerns with providers.^{34,35} While studies indicate that caregivers are fair or poor judges of PWD's pain and disregard non-verbal pain behaviors when unaided by pain assessment tools,^{20,36} recent research shows that laypersons (caregivers and non-caregivers) are able to differentiate painful from non-painful experiences effectively when provided standardized tools to facilitate behavioral observation.^{37,38} This research has predominantly been conducted in highly controlled experimental settings (observations of video-recorded actors); few studies have investigated how observational tools may be used by caregivers actively caring for PWD's in real-world clinical contexts.^{39,40} Further, while research has documented caregivers' frustration regarding pain-related communication with health care providers,^{41,42} there exist few interventions to help caregivers of PWD to articulate their pain-related concerns to medical professionals.

3. Study Design and Methods

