encourage caregivers to ask questions (e.g., increasing visit time) and ways to address those concerns (e.g. instructing caregivers to ask only questions that are of particular concern). The interviews will also address formatting considerations of the caregiver workbook and provider manual (e.g. font size, language that is easy to understand, space for notes). Caregivers will also be asked to fill out a brief questionnaire that will be sent to participants along with the PAINAD tool by email or postal mail, or given to the participant prior to their interview. The questionnaire will include demographics, caregiving role, and patient health questions. Participants will be provided a self-addressed stamped envelope to mail this survey back; or they can use the WCMC secure file transfer to email back the questionnaire.

Field testing. Once initial versions of the PICT manual and workbook are developed, they will be iteratively field-tested and vetted by family caregivers (n=25 per iteration) and health care providers (n=20 per iteration). Participants will be recruited at WCM/NYP locations including the Center on Aging and Weill Cornell Medical Associates. After reviewing the PICT workbook, caregivers will complete a brief questionnaire about the content, format, and perceived utility of PICT, as well as ways to enhance its cultural relevance. They will also complete a brief (15-20 minute) semi-structured interview to clarify their perspectives. Health care providers will answer a similar set of questions. Results from this first field-test will inform the modified version of PICT and will address key issues, such as the feasibility of using research nurses (and other practice staff) to administer the intervention, anticipation of participant burden for caregivers, and adequacy of PICT format and instructions. Study procedures will be repeated (including IRB approval) with a new sample of caregivers (n=25) and providers (n=20). Results from the second field-test will be used to create the finalized intervention of PICT. Prior research indicates that a feasible intervention should be generated after two iterations.

Pilot testing. Family caregivers will be randomly assigned to PICT (n=50) or a control (usual care) condition (n=50).

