Participants in both conditions will be asked to complete an identical pre-test questionnaire. The questionnaire will be sent to via email or postal mail, and/or will be scheduled to be completed over the phone. We will ask about the participant's background, caregiving role, and comfort speaking with health care providers. It will take approximately 15-20 minutes to complete.

Intervention condition. Participants in the intervention condition will be contacted by a member of the study team to start the PICT workbook. The PICT workbook consists of four sessions and will be completed over the telephone with a study team member. Sessions are conducted once a week and last approximately 30-60 minutes each. Participants will also be asked to read sections of the PICT workbook and complete exercises between sessions. The reading and exercises will take 10-15 minutes to complete. After the final session of the intervention, a study team member will contact the participant by telephone to complete another set of questionnaires (at 12 weeks after the pre-test questionnaire). The questionnaire will be sent to via email, postal mail, or will be scheduled to be completed over the phone. The post-test questionnaires will take approximately 20 minutes to complete and will ask about the participant's comfort and confidence in communicating with health care providers, behaviors he or she observes in the recipient, and views of the PICT workbook. Participants will also be asked to participate in a 20-30 minute telephone interview to elaborate their responses to the questionnaire. Participants must agree to be audiotaped to participate in the study.

Control condition. Caregivers in the control condition will receive an informational pamphlet about pain in dementia and a link to the Alzheimer's Association website. Twelve weeks after the participant completes the pre-test questionnaire, she or he will be contacted by a member of the study team to complete the post-test questionnaire. The questionnaires will be sent via email, postal mail, or will be scheduled to be completed over the phone and will take approximately 20 minutes to complete.

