3.2 Interviews, Focus Groups, Surveys, and/or Observations

A. Administration

- *Timing and Frequency*
 - Interview and field-testing phases: Caregiver and healthcare professional subjects will complete a one-time 20-30 minute interview accompanied by a brief questionnaire. Interviews will be conducted by a research nurse or trained co-investigators.
 - Pilot testing phase: PICT will consist of 4 weekly 30-60-minute sessions delivered by a study team member. In between sessions, participants will have 10-15 minutes of reading and exercises to complete.
- *Location*

Interview and field testing phases will take place in-person in private offices at WCMC/NYP or over the telephone. The participant, in special circumstances (e.g. scheduling issues) may opt to have the interview take place in a private location convenient to them.

Pilot testing will take place over the telephone.
- *Procedures For Audio And Visual Recording*

All interviews will be recorded and transcribed by a certified, secure, and WCM-approved transcription agency.
- *Person Identifiers*

Co-investigators may review EPIC to identify potential participants who meet eligibility. Contact information and appointment information will also be collected for either in-person or letter (postal and email) recruitment. Only data from potential participants will be stored on secure servers. These data will be deleted upon completion of the study or immediately if a patient chooses not to participate in the study.

B. Study Instruments

Interview Phase 1

- Caregiver subjects
 - Screening questions
 - Caregiving questions
 - Brief cognitive screener (BOMC)
 - Brief Questionnaire – Caregiver
 - Demographics
 - Caregiving Questions
 - Patient Health Characteristics
 - Interview Guide – Caregiver
 - Field test questions - Caregiver
- Healthcare Professional subjects
 - Brief Questionnaire – Provider
 - Demographics
 - Medical practice questions
 - Interview Guide – Provider
 - Field test question – Provider

Pilot Test Phase

- Caregiver subjects in PICT (intervention) group
 - Pre-test Questions for All Caregiver Participants
 - Post-test Questions for Caregivers in PICT Group
 - Exit Interview Questions
- Caregiver subjects in control group
 - Pre-test Questions for All Caregiver Participants
 - Post-test Questions for Caregivers in Control Group

4. Study Design

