6.1 Schedule of Assessments

Table 1. Schedule of trial events for interview and field testing phases

	Pre-study	Visit 1 (Interview)
Screening	X	
Informed Consent	X	X
Demographics and Questionnaire		X
Semi-structured Interview		X

Table 2. Schedule of trial events for the pilot test phase

	Pre-study	Week 1	Week 2	Week 3	Week 4	Post-study
Screening	X					
Informed Consent	X					
Demographics and Pre-test Questions		X				
Weekly Session *		X	X	X	X	
In-home reading *		X	X	X	X	
Post-test Questions						X
Exit Interview *						X

* denotes intervention participants only

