7.2.5 Record Retention

Essential documents are those documents that individually and collectively permit evaluation of the study and quality of the data produced. After completion of the study, all documents and data relating to the study will be kept in an orderly manner by the Investigator in a secure studyfile. Essential documents should be retained for 2 years after the final marketing approval in an ICH region or for at least 2 years since the discontinuation of clinical development of the IP. In addition, all subject medical records and other source documentation will be kept for the maximum time permitted by the hospital, institution, or medical practice.

8. Statistical Considerations

Interviews: Interview transcripts will be analyzed according to the constant comparative method, in which new concepts are compared to existing codes (labels that catalog key concepts), existing codes are refined, and a coding structure is developed in stages. This process will continue until theoretical saturation is reached - the point at which no new information is generated from additional interviews.

Pilot testing: statistical considerations. Feasibility will be examined in terms of rates of recruitment and number of sessions completed by participants in the intervention condition. Preliminary analyses to compare the intervention vs. control group on PWD and caregiver sociodemographic characteristics will be carried out in linear models (for continuous variables) and logistic-linear models (for categorical variables). The effectiveness of the intervention will be evaluated in a statistical model that includes treatment (control vs. intervention) and time of assessment (baseline vs. 4 weeks post intervention) as fixed classification factors; the interaction of treatment and time; covariates such as age and gender; and family caregivers (30 per treatment group) as levels of a random classification factor. The primary dependent variable (caregiver contacts primary care practice) is dichotomous, and analysis is by a logistic-linear mixed model with binomial error. Self-efficacy will be included in the model as a fixed classification factor (categorized in 2 levels) as will its interaction with treatment and time. Interactions with other key sociodemographic and clinical variables will also be examined.

9. Adverse Event Reporting Requirements

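### Hypothesis 3 claims superiority over an attention control, but the randomised comparator is usual care plus a pamphlet and web link, with no staff contact described between pre-test and the 12-week post-test

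*Combined protocol and SAP*

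**What the plan says.** Section 1.1.2, Hypothesis 3: "PICT will be more effective than an attention control for improving" caregivers' identification of pain and their pain-related communication with providers. The term attention control appears nowhere else in the document and is not defined.

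Section 3.1 (Pilot testing) names the arm opposite PICT differently: "a control (usual care) condition (n=50").

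Section 3.1 (Control condition) says what that arm gets: "Caregivers in the control condition will receive an informational pamphlet about pain in dementia and a link" to a dementia charity's website. The next contact it describes is the post-test: "Twelve weeks after the participant completes the pre-test questionnaire, she or he will be contacted by a member of the study team".

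Section 3.1 (Intervention condition) gives PICT four telephone sessions with a study team member: "Sessions are conducted once a week and last approximately 30-60 minutes each". Section 3.2 agrees: "PICT will consist of 4 weekly 30-60-minute sessions delivered by a study team member".

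Section 6.1, Table 2, stars the weekly session, the in-home reading and the exit interview. The star "denotes intervention participants only".

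Section 4.4 pays both arms 10 dollars for the pre-test and 30 dollars for the post-test. It pays the PICT arm a further 10 dollars for each of the four sessions.

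Section 8 evaluates effectiveness in "a statistical model that includes treatment (control vs. intervention") and does not describe the control.

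**The concern.** The comparator defines what a superiority claim means. Hypothesis 3 is the only hypothesis that compares the arms; Hypotheses 2a and 2b are benchmarks for feasibility and acceptability. It names a comparator that the design sections do not describe.

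An attention control is ordinarily included so that a difference between arms can be credited to the content of the intervention rather than to time spent with staff. Against usual care plus a pamphlet, content and contact arrive together in one arm and cannot be separated. The primary dependent variable in Section 8 is whether the caregiver contacts the primary care practice, and the post-test also asks about comfort and confidence in communicating with providers. It is plausible that repeated calls from staff could move such outcomes. That is a judgement; the documents give no estimate.

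At stake is the wording of the conclusion. A report that repeated Hypothesis 3 after a positive result would misdescribe the control arm and claim more than the contrast can show.

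**Working it through.** The plan states no figure to reproduce here. The check sets the sections side by side and adds up the scheduled contact.

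**Step 1: how each section describes the comparator.**

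| Place | Comparator |
|---|---|
| Section 1.1.1, Objective 3 | none named |
| Section 1.1.2, Hypothesis 3 | attention control |
| Section 3.1, Pilot testing | usual care |
| Section 3.1, Control condition | pamphlet and web link, then post-test at 12 weeks |
| Section 6.1, Table 2 | weekly sessions for the intervention arm only |
| Section 8 | control, not described |

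Only Hypothesis 3 refers to attention. The sections that describe the control arm agree with one another, and Section 8 does not settle which comparator is meant.

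**Step 2: staff contact between pre-test and post-test.** Inputs: 4 sessions of 30 to 60 minutes (Sections 3.1 and 3.2).

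- PICT: 4 × 30 = 120 minutes, to 4 × 60 = 240 minutes, for a caregiver who completes all sessions.
- Control: none described.

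Reading is not counted, because it is not staff contact. The exit interview is not counted, because it follows up the post-test answers.

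**Step 3: contact common to both arms.** The eligibility screening call, the consent discussion (by telephone under the oral procedure in Section 7.2.3) and the pre-test, which may be done by telephone, apply to everyone. Staff contact both arms for the post-test. None of this narrows the gap in Step 2.

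**Step 4: payment (Section 4.4).**

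- PICT: 10 + 30 + 4 × 10 = 80 dollars if all sessions are completed.
- Control: 10 + 30 = 40 dollars.
- Difference: up to 80 − 40 = 40 dollars.

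**Step 5: what the contrast estimates.** The two arms differ in PICT content, in 120 to 240 minutes of staff contact and in up to 40 dollars of session payments. The treatment term in Section 8 carries all three. There is no third arm and no measure of contact in the model that could separate them.

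**The case against.** The strongest reply is that this is one label, used once, in a pilot. Section 3.1 says plainly what controls receive, so a careful reader would not be misled about what was compared. The aim is preliminary efficacy, not a confirmatory test that isolates content from contact. Controls also get something beyond bare usual care, so the term may simply be a loose name for the pamphlet arm.

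Much of this stands. The fault is confined to the stated claim, and the term is undefined, so the conclusion depends on reading it in its ordinary sense. The reply does not remove the contradiction: the protocol itself calls the arm usual care, and a pamphlet and link do not match four staff sessions. A pilot's stated hypothesis also shapes how its result is reported and carried forward.

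A reader might infer three stronger things that the documents do not support:

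- **That controls have no staff contact at all before the post-test.** They have screening and consent contact, and possibly a telephone pre-test. After the pre-test, contact is not described but is not expressly excluded either; that none occurs is an inference from Section 3.1 and Table 2.
- **That the trial's comparison is invalid.** It is a valid randomised comparison of PICT with usual care plus pamphlet and link. Objective 3 names no comparator and is unaffected.
- **That a positive result would merely reflect attention.** The 120 to 240 minutes is a difference in exposure. The documents do not say how far contact alone would move any outcome, so no bias can be calculated.

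**Conclusion.** The point holds as a contradiction between the stated hypothesis and the design. The trial can support superiority of the PICT package over usual care plus a pamphlet and web link. It cannot support superiority over an attention control. The arms differ by 120 to 240 minutes of scheduled staff contact per caregiver completing all sessions, against none described for controls over the same period, and by up to 40 dollars in payment.

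Two assumptions carry this: that attention control means a comparator with similar contact, and that the absence of any described contact with controls after the pre-test means that none is planned. The label mismatch itself needs neither. Correction is worthwhile because it changes what may be concluded, but the matter does not threaten the validity of the trial.

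Two other discrepancies lie in the same sections: 50 against 30 caregivers per group, and a post-test 12 weeks after pre-test against one 4 weeks after the intervention. They are separate, and nothing here depends on them.

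**What to change.** State which comparator was intended, and reconcile Section 1.1.2 with Section 3.1 and Table 2.

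By default:

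- In Hypothesis 3, replace the attention control with *usual care plus an informational pamphlet and web link*, leaving the rest of the sentence as it is.
- Use that arm name in Sections 1.1.2, 3.1 and 8.
- Limit conclusions to the whole PICT package (content, staff contact and session payments) against that comparator.

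The cost is a slightly weaker stated claim and a protocol amendment, which Section 7.2.1 requires to be recorded, signed and approved by the IRB before it takes effect. The arms, the model and the sample size do not change.

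If an attention control was in fact intended, Section 3.1 and Table 2 must describe the contact that controls receive. That route costs more: it changes the control arm and adds staff time.

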3.1 Overall Design

This study includes the following phases: 1) intervention manual development; 2) Interviews; 3) field-testing; and 4) pilot randomized trial.

Manual development: The Pain Identification and Communication Toolkit (PICT) will be documented in a manual for health care providers and a workbook for caregivers. The provider manual will provide instruction on using the Pain in Advanced Dementia (PAINAD) assessment tool to detect pain in persons with dementia (PWD) and education on specific strategies to promote effective communication between family caregivers and providers, with an emphasis on fostering culturally competent interactions with PWD and their caregivers. The caregiver workbook will include instructions for how to identify pain symptoms using the PAINAD, information on differentiating between pain and dementia symptoms, strategies for effective communication with health care providers, as well as a Question Prompt List (QPL) to help facilitate action planning and culturally appropriate medical visit interactions. A research team comprised of two geriatricians, a geriatric nurse, a gerontologist, and developmental psychologist with extensive experience in conducting research in area of clinical communication will assemble the initial versions of the provider manual and caregiver workbook.

Interviews: As part of the manual development, interviews will be conducted with family caregivers (n=25) and health care providers (n=20) in-person in private offices at WCMC/NYP or over the telephone. The participant, in special circumstances (e.g. scheduling issues) may opt to have the interview take place in a private location convenient to them. All interviews will be recorded and transcribed by a certified, secure, and WCM-approved transcription agency. Participants will be recruited at WCM/NYP locations including the Center on Aging and Weill Cornell Medical Associates. Participants may also be recruited from WCM/NYP geriatric and palliative care support groups. The primary objectives of the interviews are to: a) adapt the PAINAD for use with caregivers by asking them to comment on its format and content; and b) generate an initial question pool for the Question Prompt List (QPL). The secondary objective of elucidating concerns about using a QPL to

encourage caregivers to ask questions (e.g., increasing visit time) and ways to address those concerns (e.g. instructing caregivers to ask only questions that are of particular concern). The interviews will also address formatting considerations of the caregiver workbook and provider manual (e.g. font size, language that is easy to understand, space for notes). Caregivers will also be asked to fill out a brief questionnaire that will be sent to participants along with the PAINAD tool by email or postal mail, or given to the participant prior to their interview. The questionnaire will include demographics, caregiving role, and patient health questions. Participants will be provided a self-addressed stamped envelope to mail this survey back; or they can use the WCMC secure file transfer to email back the questionnaire.

Field testing. Once initial versions of the PICT manual and workbook are developed, they will be iteratively field-tested and vetted by family caregivers (n=25 per iteration) and health care providers (n=20 per iteration). Participants will be recruited at WCM/NYP locations including the Center on Aging and Weill Cornell Medical Associates. After reviewing the PICT workbook, caregivers will complete a brief questionnaire about the content, format, and perceived utility of PICT, as well as ways to enhance its cultural relevance. They will also complete a brief (15-20 minute) semi-structured interview to clarify their perspectives. Health care providers will answer a similar set of questions. Results from this first field-test will inform the modified version of PICT and will address key issues, such as the feasibility of using research nurses (and other practice staff) to administer the intervention, anticipation of participant burden for caregivers, and adequacy of PICT format and instructions. Study procedures will be repeated (including IRB approval) with a new sample of caregivers (n=25) and providers (n=20). Results from the second field-test will be used to create the finalized intervention of PICT. Prior research indicates that a feasible intervention should be generated after two iterations.

Pilot testing. Family caregivers will be randomly assigned to PICT (n=50) or a control (usual care) condition (n=50).

Participants in both conditions will be asked to complete an identical pre-test questionnaire. The questionnaire will be sent to via email or postal mail, and/or will be scheduled to be completed over the phone. We will ask about the participant's background, caregiving role, and comfort speaking with health care providers. It will take approximately 15-20 minutes to complete.

Intervention condition. Participants in the intervention condition will be contacted by a member of the study team to start the PICT workbook. The PICT workbook consists of four sessions and will be completed over the telephone with a study team member. Sessions are conducted once a week and last approximately 30-60 minutes each. Participants will also be asked to read sections of the PICT workbook and complete exercises between sessions. The reading and exercises will take 10-15 minutes to complete. After the final session of the intervention, a study team member will contact the participant by telephone to complete another set of questionnaires (at 12 weeks after the pre-test questionnaire). The questionnaire will be sent to via email, postal mail, or will be scheduled to be completed over the phone. The post-test questionnaires will take approximately 20 minutes to complete and will ask about the participant's comfort and confidence in communicating with health care providers, behaviors he or she observes in the recipient, and views of the PICT workbook. Participants will also be asked to participate in a 20-30 minute telephone interview to elaborate their responses to the questionnaire. Participants must agree to be audiotaped to participate in the study.

Control condition. Caregivers in the control condition will receive an informational pamphlet about pain in dementia and a link to the Alzheimer's Association website. Twelve weeks after the participant completes the pre-test questionnaire, she or he will be contacted by a member of the study team to complete the post-test questionnaire. The questionnaires will be sent via email, postal mail, or will be scheduled to be completed over the phone and will take approximately 20 minutes to complete.

When caregivers express interest in the study through any recruitment method; they will be called and will be screened for eligibility which includes questions about care hours, length of care, distance, enrolled in hospice, access to internet, and must be cognitively intact (BOMC \leq 10). Any study data collected for potential participants that do not meet eligibility will be immediately deleted. Informed Consent and HIPAA authorization for caregivers and informed consent for providers will occur in-person at recruitment sites (by paper or REDCap), remotely (by mail, secure file transfer, or REDCap), or just prior to in-person interviews as outlined in the Informed Consent section. These processes will be the same for all phases of the study.

